4.0 Study Endpoints*

4.1 Describe the primary and secondary study endpoints.

The primary endpoint is to develop the B-SWELL intervention for midlife Black women using theory-based research, community engagement, and CBPR methods.

The secondary endpoint is to decrease stress and eliminate barriers to the adoption of healthy lifestyle behaviors in midlife Black women, ultimately reducing CVD risk in this vulnerable population.

4.2 Describe any primary or secondary safety endpoints.

N/A

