2.0 Objectives*

2.1 Describe the purpose, **specific aims**, or objectives.

Purpose: The purpose of this research is to develop a midlife **B**lack women's **Stress**-reduction **WELL**ness intervention, **B-SWELL**, to promote healthy lifestyle behaviors based on the stressors and themes identified in the PI's preliminary research and consistent with the American Heart Association's *Life Simple 7 Success Plan (LS7) behaviors*.

Aim 1: Develop the B-SWELL intervention for midlife Black women through the innovative leveraging of CBPR methodology and LS7 modifiable healthy lifestyle behaviors.

- a) To develop components of the B-SWELL intervention prototype for midlife Black women.
- b) Obtain ratings of the new components of the B-SWELL from an expert panel consisting of four midlife Black women laypersons, three researchers and three integrative health care specialists for degree of accuracy, relevance, and feasibility to inform further refinements.

Aim 2: Determine the feasibility of the B-SWELL intervention with a trial of 50 midlife Black women randomized to the B-SWELL intervention (25) or to a wellness education (WE) control group (25):

- a) Obtain recruitment, retention, treatment fidelity ratings, and satisfaction ratings for the intervention procedures for both groups, including technology;
- b) Compare mediator measures (stress, self-efficacy) for participants in the B-SWELL intervention group with those in the WE group at 8 and 12 weeks.
- c) Compare outcome measures (LS7 summary scores, unhealthy days, general health, depressive symptoms) for participants in the B-SWELL intervention group with those in the WE attention control group at 8 and 12 weeks.
- 2.2 State the hypotheses to be tested.

Our hypothesis proposes that B-SWELL (intervention) participants will show improved self-efficacy in managing life stress and adopting the LS7 behaviors, compared to an attention control group (WE group) receiving traditional wellness education.

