Tablets will be programmed with content and links relevant to the B-SWELL study and appropriate restrictions. Programming will be conducted by the B-SWELL research team under guidance of UC CATER staff. All study materials, including tablets, will be handled in accordance with UC COVID-19 protocols (i.e. gloves and masks).

• All drugs and devices used in the research and the purpose of their use, and their regulatory approval status.

N/A

• The source records that will be used to collect data about subjects. (Attach all surveys, scripts, and data collection forms.)

All study data and tracking will be entered into an electronic data system, REDCap (www.REDCap.org), a secure research electronic data management system with validated data entry, audit trails for tracking data manipulation, and export procedures. It is HIPAA complaint satisfying all local, state, and federal regulation for the capture and storage of private health information for research purposes.

Zoom accounts have been purchased by the UC CON. Zoom accounts will be supported by the UC CON CATER technology experts. Zoom links have been determined to be secure and appropriate for research by the UC depart of research. Members of the B-SWELL research team will be trained in the use and management of online Zoom group sessions, privacy, and technical issues.

The surveys used to collect data are included in the chart below and attached.

Construct	Survey Tool	Time	Baseline	8wks	12wks
Moderators	Demographic data: income, marital status, children, education, health problems, and community of residence (among others).	5	Х		
Mediator	Cohen's Perceived Stress Scale (PSS-10): measures perception of general stress. Items are rated on a scale of $0-4$ (Max score =40). ^{66,67} Higher stress levels correspond with higher scores.	5	X	Х	X
Mediator	General Self-Efficacy Scale (GSE): 10-item psychometric scale that assesses optimistic self-beliefs to cope with life demands ^{.68}	5	Х	Х	Х
Primary Outcome	AHA Life's Simple 7 (LS7): developed to promote cardiovascular health in accordance with the organization's 2020 Impact Goals. ⁶⁹ Risk behaviors scored 0 to 2. Higher scores indicate trend towards optimal health behaviors and lower risk for CVD.	5	X	X	X
Secondary Outcome	Number of Unhealthy Days (UD): Number of days in past month participant felt physical/mental health was not good. ⁷⁰	2	Х	Х	Х

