17.0 Data Management* and Confidentiality

17.1 Describe the data analysis plan, including any statistical procedures or power analysis.

In Aim 1 and Aim 2a, numerical measures will be summarized using descriptive statistics (i.e., means, standard deviations, and frequencies) regarding expert ratings of degrees of accuracy, relevance and feasibility of new components of the B-SWELL program (Aim 1), and recruitment, retention, treatment fidelity ratings, and satisfaction ratings (Aim 2a). For Aims 2b and 2c, numerical dependent variables (stress, self-efficacy, LS7 scores, unhealthy days, perceived general health, depressive symptoms) will be inspected of empirical distributions to ensure they meet conditions for parametric statistical models. Variable transformation will be used otherwise. All statistical tests will be performed using SPSS Version 25. Parameter estimates with P-values less than .05 will be considered statistically significant. Assumptions related to each statistical test used will be checked using residual plots, qq-plots, and tests for homogeneity of variance/ covariance. In Aim 2b, continuous mediators (stress, self-efficacy) will be compared between groups (B-SWELL vs WE) using t-tests at each visit (baseline, 8 weeks, 12 weeks).

In Aim 2c, using mixed effect models, primary (i.e., LS7 summary scores) and secondary outcome measures (i.e., unhealthy days, perceived general health, depressive symptoms) will be assessed for their associations with time (baseline, 8 weeks, 12 weeks), group (B-SWELL vs. WE), and interaction. In particular, each of the outcome measures will be treated as the dependent variable, and the time effect, group effect, and the interaction will be treated as independent variables or fixed effects of interest in the mixed effect model. Random effects will be used to account for within person correlation due to repeated measurements. Other covariates, such as demographics and attendance rate, will be controlled for by including them in the model and checking for their interaction with the intervention. Post hoc analysis of group means will be compared cross-sectionally, as well as longitudinally between time points (such as week 8 or 12 vs. baseline). Considering the limited sample size for this pilot-type of study, statistical tests will not be adjusted for multiple comparisons in post hoc analyses. Significant findings will be considered preliminary in nature and inspire future research.

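### Section 4.1, the hypothesis in 2.2 and the outcome table with 17.1 disagree on the lead participant-level outcome (stress, self-efficacy or LS7), and no follow-up visit or contrast is named as lead.

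*Combined protocol and SAP*

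**What the plan says.** - **Section 4.1.** The first endpoint is development work: "The primary endpoint is to develop the B-SWELL intervention for midlife Black women". The second is the only one that concerns participants: "The secondary endpoint is to decrease stress and eliminate barriers to the adoption of healthy lifestyle behaviors". It gives no instrument, visit or summary measure.
- **Section 2.2.** The only hypothesis is that B-SWELL "participants will show improved self-efficacy in managing life stress and adopting the LS7 behaviors", relative to the WE group. It gives no visit.
- **Survey table, section 6.** The LS7 row ("AHA Life's Simple 7 (LS7): developed to promote cardiovascular health") is labelled the primary outcome. PSS-10 (stress) and GSE (self-efficacy) are labelled mediators. Unhealthy days, general health and PHQ-9 are labelled secondary.
- **Section 17.1.** It agrees with the table, referring to "primary (i.e., LS7 summary scores) and secondary outcome measures". These outcomes get a mixed model with time, group and interaction. Stress and self-efficacy get t-tests at baseline, 8 weeks and 12 weeks.
- **Aims 2b and 2c.** Both compare the arms at both follow-up visits; Aim 2c sets B-SWELL against those "in the WE attention control group at 8 and 12 weeks". Neither visit has priority.
- **Decision rule, section 17.1.** Tests are two-sided at 0.05, without multiplicity adjustment in post hoc analyses. Significant results are to be treated as preliminary, with more weight on trends than on significance.

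**The concern.** A reader who asks which between-arm result this pilot is meant to show gets three answers: stress from 4.1, self-efficacy from 2.2, and LS7 from the table and 17.1. The passages conflict; the plan is not merely silent. LS7 does not appear in the section that defines endpoints. The barriers named there are not tied to any instrument in the survey table.

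The analysis follows the same split. The measures that 4.1 and 2.2 put forward get the weaker analysis, separate t-tests at each visit, while LS7 gets a repeated-measures model. Because no visit or contrast leads, even a reader who accepts LS7 cannot tell which LS7 result comes first.

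Section 6.1 says the findings will be used to support a larger trial, and section 8.1 says results will be posted publicly. If the lead result can be settled after the data are seen, the signal carried forward may be the most favourable of several.

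**Working it through.** **1. The plan's own power figures.** Inputs from 17.1: 25 per group, two-sided 0.05, 85% power at effect size 0.87 (two-group t-test) and 0.63 (paired t-test). Using the noncentral t distribution:

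- Two-group: df = 48, noncentrality = 0.87 × √(25/2) = 3.08, power = 0.854.
- Paired: df = 24, noncentrality = 0.63 × √25 = 3.15, power = 0.856.

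Both figures reproduce and are not in dispute. They apply to a single comparison.

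**2. The passages side by side.**

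| Measure | 4.1 | 2.2 | Survey table | 17.1 |
|---|---|---|---|---|
| Stress (PSS-10) | only participant-level endpoint | context for self-efficacy | mediator | mediator, t-tests |
| Self-efficacy (GSE) | not named | the hypothesis | mediator | mediator, t-tests |
| LS7 | not named | object of self-efficacy | primary | primary, mixed model |
| Unhealthy days, general health, PHQ-9 | not named | not named | secondary | secondary, mixed model |

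Three measures are put forward as the lead somewhere. The three in the last row never are.

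**3. Size under independence.** For k independent tests at 0.05 with no true effect, the chance of at least one P<.05 is 1 − 0.95^k.

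- Three contested measures × two follow-up visits: k = 6, 1 − 0.95^6 = 0.265.
- LS7 only, visit left open: k = 2, 1 − 0.95^2 = 0.0975.
- One named measure and visit: 0.05.

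**4. Size under correlation.** The documents give no correlations, so these are assumptions: 0 to 0.7 between measures, 0.5 or 0.8 between visits. Each setting was simulated 20,000 times with two-sample t-tests, 25 per group and normal data.

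- Six tests: 0.253 (measures uncorrelated, visits 0.5) down to 0.163 (measures 0.7, visits 0.8).
- LS7 at two visits: 0.089 (visits 0.5) and 0.079 (visits 0.8).

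**5. What the visit-wise t-tests give up.** If r is the correlation between baseline and follow-up, adjusting for baseline multiplies the variance of the arm difference by about 1 − r². Taking r = 0.5 to 0.8 as an assumption gives 1 − 0.25 = 0.75 down to 1 − 0.64 = 0.36. The baseline values are already scheduled for collection.

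**The case against.** The best defence has four parts.

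- **One causal chain.** Section 3.3.2 treats self-efficacy as a mediator of lifestyle behaviour, and the hypothesis mentions both stress and LS7 behaviours. Section 4.1 itself calls the stress entry secondary, and it reads like a programme goal. Section 3.1 describes coping with stress as a barrier to healthy behaviour, so PSS-10 could stand in for barriers. This explains how the wording arose. It does not make the labels agree: the one participant-level endpoint in 4.1 is a mediator in 17.1, and the primary outcome in 17.1 is absent from 4.1.
- **LS7 is already primary in two places.** This stands. It is why the exposure falls to at most 9.75% if 17.1 governs. The visit or contrast remains open.
- **Visit-wise Aim 2c comparisons are already post hoc.** This also stands, and the no-adjustment statement covers only post hoc analyses. But 17.1 does not say that the group-by-time interaction, or any other term, is the deciding test.
- **It is a pilot.** Findings are called preliminary, and emphasis on significance is deferred to a later trial. This lowers the consequence considerably but does not tell a reader which outcome leads.

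A reader might go further and infer that any of 12 comparisons (six measures at two visits) could be headlined, with a chance of 1 − 0.95^12 = 46% of a false positive. The documents do not support that. Unhealthy days, general health and PHQ-9 are consistently secondary, which removes six of the 12. The 46% also assumes independence; the assumed correlations give about 25–44% even for all 12. Nor do the documents say that registration requires a single primary outcome and time point; section 8.1 says only that the study will be registered and results submitted.

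**Conclusion.** The inconsistency is real and should be corrected. Three measures compete as the lead participant-level outcome, and neither follow-up visit nor any contrast is designated. The chance of at least one nominally significant result among the contested comparisons, with no true effect, is up to 26% (about 16–25% under the assumed correlations). If 17.1 is taken to override 4.1 and 2.2, it is up to 9.75% (about 8–9%). Both exceed the 5% of a single named test.

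These figures treat every comparison as a two-sample t-test at a follow-up visit with 25 per group. The correlations are assumptions. The plan's exploratory stance keeps this short of a critical flaw, and its power figures are unaffected. Separately, the visit-wise t-tests for stress and self-efficacy use the data less well than the model already planned for LS7.

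**What to change.** 1. **Section 4.1.** Keep development and feasibility as the main objectives; feasibility is the stated Aim 2 objective but is missing from 4.1. Name the LS7 summary score, as the table and 17.1 already do, as the lead efficacy outcome, with one visit or group-by-time contrast fixed before data are seen. Eight weeks, the end of the intervention, is one reasonable choice; the documents do not favour it over 12, so the sponsor should decide.
2. **Other comparisons.** Label all other between-arm comparisons secondary or exploratory. Keep stress and self-efficacy as mediators.
3. **Barriers.** Remove their elimination as an endpoint, or tie it to a named instrument.
4. **Section 2.2.** Align the hypothesis with the lead outcome and the mediator roles.
5. **Section 17.1.** Analyse stress and self-efficacy with the same repeated-measures mixed model as Aim 2c, with baseline as a covariate or a common baseline mean, in place of separate t-tests.

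The cost is wording in 2.2, 4.1 and 17.1, plus two more models on data already scheduled. No participants or visits are added, and the stated 85% power at 0.87 stands for the lead test if it is a two-group comparison at one visit. Adjusting instead is costly: Bonferroni over all 12 between-arm comparisons (0.05/12 = 0.0042 each) would cut power at 0.87 to 53%. The downside is that a significant result on another measure or visit must be reported as secondary or exploratory.

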5.0 Study Intervention/Investigational Agent

5.1 FDA-Related, Select Applicable:

	Drugs or Biologics	The proposed research involves the administration of an article (e.g. drug, biologic, herbal preparation, dietary supplement, etc.) to a human where the article is intended for use in the diagnosis, cure, mitigation, treatment, or prevention of disease or is intended to affect the structure or any function of the body. For both FDA and non-FDA approved article.
	Devices	Any research that involves the use of a device (medical or other devices, approved or investigational) to test the safety or effectiveness of the device or the device is the focus of the research. Note: This includes research that will use human samples to test the safety or effectiveness of a device.
	Data Collection	Any research that involves the collection of data or other results from individuals that will be submitted to, OR held for inspection by, the FDA. In general this would include research that involves any data that will be provided (in any form) to a pharmaceutical, medical device or biotech company.
	Specimens	Any research activity where specimens (of any type) from individuals, regardless of whether the specimens are identifiable, are used to test the safety or effectiveness of any device (medical or other devices, approved or investigational) and the information will be submitted to, or held for inspection by, the FDA.
\boxtimes	None of the Above	None of the above describes my research.

1.1

1.2 Describe the study intervention and/or investigational agent *(e.g., drug, device)* that is being evaluated.

N/A

5.2 Drug/Device Handling: If the research involves drugs or device, describe your plans to store, handle, and administer those drugs or devices so that they will be used only on subjects and be used only by authorized investigators.

N/A

5.3 If the drug is investigational (has an IND) or the device has an IDE or a claim of abbreviated IDE (non-significant risk device), include the following information: N/A

6.0 Procedures Involved*

6.1 Describe and explain the study design.

This is a development and feasibility study. It will take place in two parts as outlined in Aims 1 & 2. In accordance with Aim 1, we will develop a stress reduction wellness intervention for midlife Black women and rate its accuracy, relevance, and feasibility using an expert panel and a community research

advisory board. We will then pilot the intervention using a sample of 50 women randomized to either the B-SWELL group or the WE (attention control) group. Satisfaction ratings will be obtained from participants. The study findings will be used to determine feasibility of the intervention and support a larger trial.

6.2 Provide a description of all research procedures being performed and when they are performed, including procedures being performed to monitor subjects for safety or minimize risks.

6.2.1 Methods for Aim 1

Aim 1: Develop the B-SWELL intervention for midlife Black women through the innovative leveraging of CBPR and LS7 modifiable healthy lifestyle behaviors. In Aim 1, the content for both the intervention (B-SWELL) and control groups (WE) will be developed. The B-SWELL intervention is proposed as an 8-week community-based intervention, culturally tailored to decrease stress in midlife Black women while simultaneously addressing key risk factors associated with CVD (Figure 1). The B-SWELL program will address key stressors and cultural themes identified in the PI's preliminary research ^{8,9} to provide a unique approach tailored to midlife Black women. Each module in the 8-week intervention will focus on the adverse effects of stress on health, in particular CVD, and the importance of minimizing these effects through healthy lifestyle behaviors (LS7). Links will be drawn between stress and CVD risk factors such as lack of exercise, poor diet, smoking, sleep deprivation, and non-adherence to treatment regimens. Stress reduction strategies included in the B-SWELL will be presented with emphasis on the needs and preferences of midlife Black women. For example, culturally relevant images will be used in guided imagery exercises. The tools learned in the B-SWELL will enable participants to be self-directed and create personalized plans to adopt healthy lifestyle behaviors. Content will be delivered by lecture, demonstration, and interactive exercises to increase engagement and promote inclusivity.

Consider this scenario: a midlife Black woman desires to improve her health and lifestyle habits. Through the B-SWELL program, she gains an understanding of how personal beliefs, culture, and socialized expectations inform her lifestyle decisions and affect her risk factors for CVD. She learns strategies to address the key stressor in her life: poor life balance. She receives support and validation from other participants in the program and takes steps to adjust her schedule and make time for exercise. She joins a carpool at her daughter's school that frees her up 2 times a week to participate in a morning walking group while also allowing her extra time in the afternoon to relax before her daughter and husband return home. Empowered by this positive change, she decides that she will next create a personalized plan to stop smoking.

Collaboration with the West End C-RAB and other community partners is critical to Aims 1 & 2. In CBPR, the community is recognized as a vital stakeholder to be included at every stage of the research. The C-RAB's participation will ensure that the B-SWELL reflects the needs of midlife Black women. The final intervention, including its materials and processes, will reflect knowledge gained from the PI's training plan, input from community collaborators, and refinements dictated by the initial ratings.

Data Collection Procedures: Aim 1. Data collection will occur during the development phase in Aim 1. Data will be collected using survey ratings about materials and components of the B-SWELL intervention from 10 identified experts. The expert panel will include four midlife Black women laypersons, three researchers (identified as experts by having a doctoral degree and strong record of publication), and three integrative health care specialists. Rating surveys will be similar to those used by [name] in her feasibility study 22 to assess accuracy, relevance, and feasibility. Ratings will be averaged across the experts, with possible scores ranging from 1=strongly disagree to 5=strongly agree.

Recruitment and Informed Consent. Following approval from the UC IRB, research activities will begin. In Aim 1, the intervention will be developed and expert raters will be recruited to assess and evaluate the intervention materials and content. Experts will be recruited by word of mouth and by special invitation from the researchers by email, mail, telephone, or flyers. They will receive a study information sheet explaining that participation is voluntary and that their decision will not affect their relationship with the University of Cincinnati, their employer, or the researchers. Full information will be provided and questions answered prior to consent. Incentives will be provided to the experts for participation.

6.2.2. Methods for Aim 2

Aim 2: Determine the feasibility of the B-SWELL intervention with a trial of 50 midlife Black women randomized to the B-SWELL intervention (25) or to a general wellness education (WE) control group (25). Aim 2 will focus on conducting a successful trial of the 8-week B-SWELL intervention for midlife Black women. The preliminary conceptual model in Figure 2 will guide this phase of the research. We anticipate that the model will be refined as we synthesize the new knowledge and feedback from the community (Aim 1). During Aim 2, community-based activities will focus on the recruitment, trial, data collection, and dissemination. Midlife Black women will be recruited and randomized into one of two groups: B-SWELL intervention group or a wellness education control group, WE group. Sessions will be held online using the Zoom online platform which has been approved and is supported by the university for research. Participants will be asked not to share intervention materials or experiences with midlife Black women outside of their assigned group. Participants in both groups will be introduced to AHA's LS7 behaviors, LS7 materials, and the LS7 website using B-SWELL tablets. Participants in the B-SWELL intervention group will also receive education about stress, with a focus on unique stressors experienced by midlife Black women.

Program evaluation will be ongoing. Data collection telephone interviews will occur at three time points: baseline (pre-intervention), 8 weeks (completion of the study), and 12 weeks (4 weeks post intervention) for both the B-SWELL and WE groups. Outcome measures will include LS7 scores, number of unhealthy days, depressive symptoms, and perceived general health. Ratings will be obtained from community collaborators to evaluate recruitment, retention, and treatment fidelity for both groups. Qualitative feedback and satisfaction ratings for the B-SWELL groups, WE groups, and technology will be obtained from participants at completion.

Recruitment and Eligibility: Aim 2: The sample of participants for Aim 2 will consist of 50 Black or African-American women randomized to a B-SWELL group (n=25) or to a WE attention control group (n=25). Inclusion criteria include being Black or African-American, between the ages of 40 and 64, fluent in the English language, ability to hear and speak well enough to engage in everyday conversation, access to a telephone, access to WIFI and willingness to participate. Exclusion criteria include recent immigration to the U.S., prisoner or on house arrest, pregnant, terminal illness (i.e., late stage cancer, end-of-life condition, renal failure requiring dialysis), history of Alzheimer's, dementia, or severe mental illness (i.e., suicidal tendencies, schizophrenia, or severe untreated depression), or any other major health conditions or disabilities (i.e. visual impairment, blindness, deafness) prohibiting safe or full participation in the program. Recruitment will involve use of fliers, referral, snowballing, and purposeful sampling in targeted communities. Fliers may be posted in businesses, on list serves, or group websites to increase distribution. The 8-week trial will take place virtually using a Zoom account established through the UC CON for the PI. Dates and times of the online virtual sessions will be established based on availability of the participants following randomization.

Interventions and Treatment Fidelity Methods: The B-SWELL intervention will follow procedures such as those proposed in Figure 1 and will be refined prior to trial based on feedback from the community collaborators and expert ratings (Aim1). Participants will be randomized to either the B-SWELL or WE groups. Both groups will be introduced to the LS7 materials. The B-SWELL will receive additional instruction about stress. B-SWELL and WE group sessions will occur on different dates and times and, participants will be asked not to share experiences with women outside of their assigned group. Participants will also be asked to secure private location when attending the virtual sessions to ensure privacy and confidentiality. Treatment fidelity of both groups will be monitored using Borrelli's Treatment Fidelity Checklist (Design, Training, Delivery, Receipt, Enactment). Facilitators of the intervention and control groups will be trained prior to the start of the trials.. Zoom meetings will be audio taped for quality assurance.

Data Collection Procedures: Aim 2. Data collection will occur at baseline, 8 weeks, and 12 weeks. Baseline data will be collected from B-SWELL and WE participants using telephone interviews conducted by trained, blinded research assistants. Data collection at 8 and 12 weeks may be collected via phone interview or through a REDCap link on the B-SWELL study tablets provided to B-SWELL and WE participant. Completion of the surveys (interview or via REDCap link) is expected to last 30-45 minutes for each timepoint. Instruments are listed in Table 5. 3.4.d.

Randomization Procedures: Following baseline data collection, participants will be randomized to either the B-SWELL or WE group using 1:1 block randomization to promote equal group sizes. The randomization allocation sequence will be blinded to data collectors to avoid bias during follow-up data collection telephone interviews. Following randomization, the PI or research assistant will notify the participant of their group assignment and upcoming group meetings. Treatment fidelity will be monitored using the Borrelli's Treatment Fidelity Checklist (Design, Training, Delivery, Receipt, Enactment).

Recruitment and Informed Consent. In Aim 2, trial of the intervention will be conducted. Participants for the trial of the intervention will be recruited using fliers, referral, snowballing, and purposeful sampling in targeted communities. Fliers may be posted on list serves or group websites to increase distribution. A letter of introduction and study information sheet will be the first contact made for the study. A telephone number is provided for potential participants to call if they wish to participate. The PI or trained research staff will make the calls from a private location to protect confidentiality of the participant. If eligible and interested in participating, the person will be invited to participate and receive informed consent. All participants will be informed that participation in the study is voluntary, and they are free to discontinue participation at any time. Those who are eligible and who have signed the informed consent will be enrolled. The PI or research staff trained by the PI will obtain consent. Upon completion of the study, participants will receive a gift valued at \$40 and keep all study materials. Study materials will consist of a study binder, AHA and LS7 informational materials, and a Fire 8 tablet.

6.3 Describe: Procedures performed to lessen the probability or magnitude of risks.

This study has minimal risk. Some survey items asked during the phone interviews may focus on negative emotions or experiences. There is a risk of loss of confidentiality for participants involved in the study given the online Zoom platform used for each session. Audiotapes of the Zoom sessions are for quality assurance. Transcriptions will be de-identified. There are no anticipated physical, social, legal, or other potential risks connected with the proposed procedures. The alternative to participating in the study is not to participate in the study. Participants and experts may withdraw at any time or may choose not to answer items during the interviews that make them uncomfortable.

Protections against risk. Participants may choose not to answer items during interviews or participate in portions of the intervention program with which they are uncomfortable. In the unlikely event that a participant appears to be distressed, she will be referred to appropriate resources or be given the telephone number for the national Suicide [contact]; [name]) if appropriate. The PI will inform the IRB of any adverse events and/or any amendments to the protocol. Training for data collectors also will include how to respond to any potential adverse events experienced by participants, such as suicidal tendencies or severe depression. Participants with these types of problems will be given information about how to seek help and will be encouraged to inquire whether medication and/or psychological counseling would be helpful. In the event of suicidal thoughts, the PI or research staff may contact a health care provider on the participant's behalf so that they can contact the participant directly to determine if treatment is necessary.

To avoid loss of confidentiality during the online Zoom sessions, participants will be asked to find a private location from which to attend the online Zoom sessions. Additionally, participants will be required to attend Zoom sessions with video and will be asked to keep session discussions and activities private.

Only authorized study personnel will have access during the Zoom sessions, Zoom audiotapes or transcriptions, REDCap data, database, or contact information for study participants and expert panel members. For data analysis, study ID numbers will be generated to protect the identity of the participants in the final data set. Participants will not be identified in any way in reports or manuscripts from the study. Data from surveys will input directly into a REDCap database either manually or via the link on the study tablets. REDCap is backed up nightly by the university. Only authorized study personnel will have access to REDCap. Any calls to participants will be made to a telephone number provided by the participant at a time that is convenient for the

participant. Research staff will make calls from a private location in order to protect confidentiality. Informed consent forms and contact information from participants will be stored separately in a locked file cabinet to protect confidentiality.

Tablets will be programmed with content and links relevant to the B-SWELL study and appropriate restrictions. Programming will be conducted by the B-SWELL research team under guidance of UC CATER staff. All study materials, including tablets, will be handled in accordance with UC COVID-19 protocols (i.e. gloves and masks).

• All drugs and devices used in the research and the purpose of their use, and their regulatory approval status.

N/A

• The source records that will be used to collect data about subjects. (Attach all surveys, scripts, and data collection forms.)

All study data and tracking will be entered into an electronic data system, REDCap (www.REDCap.org), a secure research electronic data management system with validated data entry, audit trails for tracking data manipulation, and export procedures. It is HIPAA complaint satisfying all local, state, and federal regulation for the capture and storage of private health information for research purposes.

Zoom accounts have been purchased by the UC CON. Zoom accounts will be supported by the UC CON CATER technology experts. Zoom links have been determined to be secure and appropriate for research by the UC depart of research. Members of the B-SWELL research team will be trained in the use and management of online Zoom group sessions, privacy, and technical issues.

The surveys used to collect data are included in the chart below and attached.

Construct	Survey Tool	Time	Baseline	8wks	12wks
Moderators	Demographic data: income, marital status, children, education, health problems, and community of residence (among others).	5	Х		
Mediator	Cohen's Perceived Stress Scale (PSS-10): measures perception of general stress. Items are rated on a scale of $0-4$ (Max score =40). ^{66,67} Higher stress levels correspond with higher scores.	5	X	Х	X
Mediator	General Self-Efficacy Scale (GSE): 10-item psychometric scale that assesses optimistic self-beliefs to cope with life demands ^{.68}	5	Х	Х	Х
Primary Outcome	AHA Life's Simple 7 (LS7): developed to promote cardiovascular health in accordance with the organization's 2020 Impact Goals. ⁶⁹ Risk behaviors scored 0 to 2. Higher scores indicate trend towards optimal health behaviors and lower risk for CVD.	5	X	X	X
Secondary Outcome	Number of Unhealthy Days (UD): Number of days in past month participant felt physical/mental health was not good. ⁷⁰	2	Х	Х	Х
Secondary Outcome	Perceived General Health: Uses the general health perception item from the Short Form Health Survey (SF36). Health rated as 'excellent', 'very good', 'good', 'fair' and 'poor'. ⁷¹	2	Х	X	Х
Secondary Outcome	Patient Health Questionnaire (PHQ-9): A diagnostic instrument for depressive symptoms. Scores each of the 9 DSM-IV criteria as '0' (not at all) to '3' (nearly every day). ⁷²	5	Х	Х	Х
Program Evaluation	Satisfaction (Adapted from Satisfaction questionnaire): Measures usefulness, ease of use, and acceptability ratings.(Bakas et al., 2009)	10			Х
Technology Evaluation	Satisfaction (Adapted from Satisfaction questionnaire): Measures usefulness, ease of use, and acceptability ratings.(Bakas et al., 2009)	5			Х
Total Minutes	Total data collection minutes each visit	40 min	30 min	25 min	35 min

6.4 What data will be collected during the study and how that data will be obtained?

Rating surveys, self-report survey data, and satisfaction ratings will be gathered from the expert panel and participants (Aims 1 & 2) and entered directly into a REDCap database via laptop computer or REDCap survey link. Intake data will be labeled with study ID numbers and stored separately. Names, contact information, or any other identifiers will be stored separately from all data that is collected. Access to the database, contact information, or links between study ID numbers and participants enrolled in the study will be limited to the investigators. Participants will not be identified in reports or manuscripts from the study. All paper forms and study materials will be stored in locked file cabinets accessible only to authorized study personnel. All computers, servers, and electronic files used in the study will be password protected and accessible only to authorized study personnel. Authorized study personnel will include the investigators and research staff involved in the study.

6.5 If there are plans for long-term follow-up, what data will be collected during this period.

A third and final data collection time point will occur 4 weeks after the completion of the intervention (12 weeks).

6.6 For Humanitarian Use Device (HUD) uses provide a description of the device, a summary of how you propose to use the device, including a description of any screening procedures, the HUD procedure, and any patient follow-up visits, tests or procedures.

N/A

